#### 6.3.2.1.1.1 Minimum and maximum time to first void

The minimum and maximum time to first void will be analyzed to establish a range during which subjects are having their first void of the night.

To assess the minimum time to first void across all 3 voiding nights, variables will be derived as follows:

• Minimum time to first nocturnal void (in hours) = Minimum (Time of first nocturnal void – Bedtime) during cycles 1, 2 or 3 (by visit).

The derivation of the variable will be repeated for the maximum time to first void:

• Maximum time to first nocturnal void (in hours) = Maximum (Time of first nocturnal void – Bedtime) during cycles 1,2 or 3 (by visit).

The same derivations apply in the event of missing voiding nights, and censoring is also defined in the same way [see Section 6.3.2.1.1].

#### 6.3.2.1.2 Analysis

All analyses will be conducted based on the FAS.

# 6.3.2.1.2.1 Kaplan-Meier analysis

Kaplan-Meier summary tables and plots will be constructed separately for Week 1 and Week 4 by treatment. The number of subjects with events and censored observations will be presented by treatment and visit.

Kaplan-Meier plots at baseline will be constructed by sequence and overall.

No inferential statistics will be provided due to the dependence of the observations in this cross-over design.

The average time to first void and the changes from baseline will be summarized via descriptive statistics by treatment and visit.

# 6.3.2.2 Within-subject comparison of time to the first nocturnal void

#### 6.3.2.2.1 Variable

The time to first nocturnal void is derived as described in Section 6.3.2.1.1 (for Week 1 and Week 4). As each subject receives both treatments, a within-subject comparison of the time to first nocturnal void is performed, separately at Week 1 and Week 4, i.e., the 'preferences' (= longer average duration to first nocturnal void across 3 cycles) are summarized in a  $2 \times 2$  contingency table, as shown in Table 4. If a subject is missing data in one or both treatment periods, this subject's information is considered as missing and will not be included in the analysis. In the event of censored data, i.e., subjects that have no single void in 3 cycles, the preference will be assigned to the period where the subject was censored.

Page 26/50

Statistical Analysis Plan for Clinical Study Report Version 2 Doc No D-24.149

Table 4 Contingency table of preferences

Treatment	preference
Heatinent	preference

Treatment group	TP I	TP II	Total
Daridorexant 50 mg	х	у	x + y
Placebo	Z	a	z + a
Total	x + z	y + a	x + y + z + a

TP I/II = treatment period I/II

From this table it can be derived that (x + y) subjects prefer daridorexant 50 mg, whereas (z + a) subjects prefer placebo. The differences across periods can be observed in the total row (x + z) for TP I; y + a for TP II).

# 6.3.2.2.2 Analysis

The contingency table is analyzed separately at Week 1 and Week 4 based on the FAS via a 2-sided sign test for matched pairs. A binomial distribution will be used to compute the p-values (2-sided), which will be presented in the table.

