# Nocturia-related endpoints:

- Change from baseline to Week 1 and Week 4 in number of nocturnal voids assessed using a voiding diary;
- Change from baseline to Week 1 and Week 4 in the time to the first nocturnal void assessed using the voiding diary;
- Change from baseline to Week 1 and Week 4 in the volume of the first nocturnal void assessed using the voiding diary;
- Change from baseline to Week 1 and Week 4 in the total nighttime voiding volume assessed using the voiding diary;
- Change from baseline to Week 1 and Week 4 in number of daytime voids assessed using a voiding diary;
- Change from baseline to Week 1 and Week 4 in the total daytime voiding volume assessed using the voiding diary;

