# 6.3.2.1 Time to the first nocturnal void

#### 6.3.2.1.1 *Variable*

The variable derivation follows the approach as used by Minze Health.

The time to first nocturnal void (hours) is derived for each voiding night ('Cycle') separately as follows:

• Time to first nocturnal void (in hours) = Time of first nocturnal void (after bedtime and before waketime) – Bedtime.

Potentially, a date is required for computation of the variable if the bedtime is prior to midnight and the first void is after midnight. In the event of missing information on bedtime and/or waketime, the variable is set to missing and the data will not be included in the analyses defined below.

After derivation of the time to first nocturnal void per night (in hours), the average time to first void will also be computed across the 3 voiding nights (by visit). In the event of missing nights or nights without voids, the average will be computed based on the nights with available data.

In the event of no voiding during any of the 3 consecutive nights, the censoring time is defined as follows:

 Censoring time (in hours) = Maximum (Waketime – Bedtime) during voiding cycle 1, 2 or 3 (by visit).

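### The only treatment test for time to first nocturnal void is a sign test, which discards the size of each within-subject difference; no paired estimate in hours with a confidence interval is planned

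*SAP*

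**What the plan says.** SAP 6.3 lists the endpoint as "Change from baseline to Week 1 and Week 4 in the time to the first nocturnal void assessed using the voiding diary". SAP 6.3.2.1.1 derives it in hours for each night (first void minus bedtime) and averages it over the three diary nights, using the nights with data. Three rules limit who has a value:

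- "In the event of missing information on bedtime and/or waketime, the variable is set to missing".
- A visit with no void on any of the three nights is censored at the longest bedtime-to-waketime interval.
- In the paired comparison, the rule beginning "If a subject is missing data in one or both treatment periods" removes the subject.

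SAP 6.3.2.2.1 then reduces each pair to a preference, defined as the "longer average duration to first nocturnal void across 3 cycles". A censored period counts as the preferred one. SAP 6.3.2.2.2 tests the resulting counts: "The contingency table is analyzed separately at Week 1 and Week 4 based on the FAS via a 2-sided sign test for matched pairs". The stated output is a p-value: "A binomial distribution will be used to compute the p-values (2-sided), which will be presented in the table".

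The rest of the analysis is descriptive. Under the Kaplan-Meier heading (SAP 6.3.2.1.2.1): "No inferential statistics will be provided due to the dependence of the observations in this cross-over design". The same section adds: "The average time to first void and the changes from baseline will be summarized via descriptive statistics by treatment and visit".

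**The concern.** The sign test gives a five-minute gain and a three-hour gain the same weight. The reason given for withholding inference, dependence between observations, applies to an unpaired comparison of Kaplan-Meier curves. A paired analysis that keeps the hours deals with dependence, and the SAP uses such analyses elsewhere: an MMRM with estimate and CI for the number of nocturnal voids (6.3.2.5.2), and a paired t-test with mean and CI for treatment satisfaction (6.3.3.6).

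The baseline is the single set of nights after Visit 1 (Protocol 3.2.9), so it cancels in the daridorexant-minus-placebo difference. That difference in hours is therefore the treatment effect on the endpoint as defined.

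Two things are at stake: power on a supportive nocturia result, and an estimate, with its uncertainty, of how long the first void is delayed.

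**Working it through.** **Inputs.** From Protocol 9.4 and 9.4.1: 50 subjects, two-sided alpha 0.05; sTST difference 26 min (or 20 min) with SD 44 min; nocturnal voids difference 0.30 with SD 0.7. No effect or SD is given for time to first void. As an assumption, the standardised effects are borrowed: d = 0.30/0.7 = 0.429 and d = 26/44 = 0.591.

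**The plan's own figures first.** Paired t-test power from the noncentral t, with 49 df and noncentrality d√50:

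- sTST 26/44: 98.4% (stated: at least 90%).
- sTST 20/44: 88.3% (stated: at least 80%).
- Voids 0.30/0.7: 84.4% (stated: approximately 80%, so the statement is conservative).
- SD of the sTST difference: √(42.5² + 50.5² − 2 × 0.58 × 42.5 × 50.5) = 43.2 (stated: 44).

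**Sign test.** With 50 pairs the exact two-sided test rejects when 33 or more pairs favour one treatment. Its actual size is 2 × P(X ≥ 33 | 50, 0.5) = 0.033. Under normal differences, the probability that a pair favours daridorexant is Φ(d):

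- d = 0.429: Φ = 0.666, power 60.0%.
- d = 0.591: Φ = 0.723, power 87.4%.

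**Sign test against signed-rank, 50 pairs (simulation, 20,000 runs).**

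| Shape of differences | d | Sign | Signed-rank | Gap (points) |
|---|---|---|---|---|
| Normal | 0.429 | 60.2% | 82.6% | 22 |
| Normal | 0.591 | 87.4% | 97.8% | 10 |
| Logistic | 0.429 | 71.2% | 87.0% | 16 |
| Logistic | 0.591 | 93.6% | 98.7% | 5 |
| t, 5 df | 0.429 | 77.6% | 90.4% | 13 |
| t, 5 df | 0.591 | 96.0% | 99.2% | 3 |
| Laplace | 0.429 | 88.8% | 92.2% | 3 |
| Laplace | 0.591 | 98.7% | 99.5% | 1 |
| t, 3 df | 0.429 | 93.4% | 97.4% | 4 |
| t, 3 df | 0.591 | 99.5% | 99.9% | 0 |

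**Number of pairs.** Because the exact test is discrete, its power moves unevenly. At d = 0.429 it is 56.3% with 48 pairs, 63.9% with 49 and 60.0% with 50.

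**Unreliable void-free records.** Suppose a share of pairs is replaced by extreme differences of random sign (assumption; normal differences, d = 0.429). The signed-rank advantage falls from about 22 points to about 13 at 10% of pairs, 8 at 15% and 3 at 20%.

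**Would censoring force an order-only test?** A visit is censored only if all three nights are void-free. Entry requires a diary average of at least 2.6 voids per night and no night below 2 (Protocol 5.2, criterion 7), so true censoring should be uncommon. A signed-rank test can place such a pair at the extreme.

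**The case against.** The strongest objection concerns data quality. SAP 6.3.2.4 reports that some day, night and morning voids were mislabelled, and that a night without voids may mean either no void or no data collected. A signed-rank test that places void-free visits at the extreme could give a recording failure the largest weight; the sign test gives it one vote. This stands. The contamination check above shows the gain shrinking, and the fix has to allow for it. In addition, void-free nights are left out of the average whenever another night has a void, so an estimate in hours is conditional on the nights that enter the average.

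It is also fair to say that the sign test is valid and conservative (size 0.033) and that no decision rule depends on it. Protocol 3.5 says that endpoints other than sTST are not adequately powered, and Protocol 9.2.2 defines no secondary endpoints. Other nocturia variables, such as first-void volume, receive no inference at all. This limits the importance of the point. It does not explain why the one treatment test planned here should discard the hours.

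A reader might infer more than the documents support:

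- That every subject has a value in hours in both periods. The missing-data and censoring rules say otherwise, so a plain paired t-test is not a drop-in replacement.
- That the plan gives no information on effect size. Descriptive means and changes in hours by treatment are planned, and Table 4 shows the counts. Only the paired estimate with a CI is missing.
- That a real effect would probably be missed. At the two borrowed effects the sign test has 60% and 87% power, so significance is more likely than not. At a smaller assumed d of 0.30 it has 32%, but the signed-rank test has only 53%.

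**Conclusion.** The point holds as a cheap improvement to an exploratory analysis. The part that needs no assumption is that the plan has no within-subject difference in hours with a CI, and that its only treatment test ignores the size of each difference.

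The power loss is conditional. With borrowed effects of 0.43 to 0.59, 50 complete pairs and normal differences it is about 10 to 22 points against a signed-rank test. At d = 0.43 the chance of missing the effect is about 40% instead of about 17%. The loss drops to between 0 and 4 points for very heavy-tailed differences (Laplace, or t with 3 df) and to about 3 points at d = 0.43 if a fifth of the pairs carry random extreme values. In every distribution examined the signed-rank test did at least as well as the sign test. The documents do not show which shape applies.

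The consequence is lost precision and interpretability on a supportive nocturia result. The sTST conclusion is not affected.

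**What to change.** In SAP 6.3.2.2.2, at Week 1 and at Week 4:

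1. Make the treatment comparison a Wilcoxon signed-rank test on the within-subject difference (daridorexant minus placebo) in average time to first nocturnal void.
2. Report the Hodges-Lehmann difference in hours with its 95% CI.
3. Rank a pair censored in one period as extreme, in the direction that SAP 6.3.2.2.1 already assigns. Treat a pair censored in both periods as a tie, a case the present rule does not resolve.
4. Repeat the analysis with visits that are void-free on all nights set to missing. SAP 6.3.2.5, analysis 3, already treats void-free nights this way for the void count.
5. Keep Table 4 and the sign test as supportive.

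The cost is SAP text and a few lines of code, to be settled before the blind is broken; no new data or procedures are needed. The downside is that the signed-rank test assumes roughly symmetric differences and is more sensitive to misrecorded void-free visits. Items 4 and 5 address this.

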# 6.3.2.3 Changes from baseline to Week 1 and Week 4 in the volume of the first nocturnal void

The first nocturnal voiding volume is defined as the volume of the first nocturnal void collected after bedtime and before waketime.

The first voiding volume per night will be averaged across voiding nights. The mean first voiding volume and corresponding change from baseline will be summarized descriptively by visit and treatment.

#### 6.3.2.4 Change from baseline in total voiding volume (nighttime and daytime)

Three analyses will be conducted for the change from baseline in total nocturnal voiding volume:

- 1. Nocturnal voiding volume as derived by Minze Health (derived data are provided by Minze Health).
- 2. Derived nocturnal voiding volume, defined as cumulative voiding volume between bedtime and waketime.
- 3. Derived nocturnal voiding volume, defined as cumulative voiding volume between bedtime and waketime, excluding nights with a total voiding volume of 0.

The rationale for the conducted analyses is the partially incorrect labelling of day, night and morning voids in the Minze Health database and nights without any voids. For nights

without any voids, it is unclear whether the data were not collected or if the patient did not void at all.

Analyses for the nocturnal voiding volume **plus** the morning volume will be conducted as well, but only based on data as derived by Minze Health.

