3.4 Endpoints

It is anticipated that the collection of the voiding volume will interfere with sleep-related endpoints, therefore a staggered approach for the endpoint assessments is pursued. The details are described below and apply for each treatment period.

Information on the endpoints and their relation to the objectives is shown in Table 3.

Further details on the endpoints are described in the SAP.

Table 3Endpoints and objectives

Objectives	Endpoints in period I and period II			
To assess the efficacy of daridorexant on insomnia in subjects with insomnia and	Primary endpoint:Change from baseline to Week 4 in sTST			
comorbid nocturia	Other insomnia related endpoints:			
	• Changes from baseline to Week 1, Week 2, and Week 3 in sTST			
	• Changes from baseline to Week 2 and Week 4 in ISI [©] total score			
	• Changes from baseline to Week 1, Week 2, Week 3, and Week 4 in quality and depth of sleep as determined by scores on the VAS (mm) in the morning			
	• Changes from baseline to Week 1, Week 2, Week 3, and Week 4 in the daytime alertness and daily ability to function as determined by scores on the VAS (mm) in the evening			
	• Changes from baseline to Week 1, Week 2, Week 3, and Week 4 in mean number of self-reported awakenings based on the sleep diary			
To assess the efficacy of daridorexant on	Nocturia related:			
nocturia	• Changes from baseline to Week 1 and Week 4 in number of nocturnal voids assessed using a voiding diary			
	• Changes from baseline to Week 1 and Week 4 in the time to the first nocturnal void assessed using the voiding diary			
	• Changes from baseline to Week 1 and Week 4 in the volume of the first nocturnal void assessed using the voiding diary			
	• Changes from baseline to Week 1 and Week 4 in the total nighttime voiding volume assessed using the voiding diary			
	• Change from baseline to Week 1 and Week 4 in number of daytime voids assessed using a voiding diary			
	• Changes from baseline to Week 1 and Week 4 in the total daytime voiding volume assessed using the voiding diary			
	Change from baseline to Week 4 in ICIQ-NQoL			
	• Change from baseline to Week 4 in lower urinary tract symptoms sub-score using the ICIQ-MLUTS and FLUTS for male and female subjects, respectively			
To assess the overall patient's ratings of their condition and symptoms	• Changes from baseline to Week 1, Week 2, Week 3, and Week 4 in Patient Global Assessment of Disease Severity (daytime symptoms)			

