# 6.3.2 Analysis of nocturia-related endpoints (time to first nocturnal void; voiding volume; number of nocturnal voids)

The Minze Diary Pod [Bladt 2022] consists of a voiding pod and a voiding diary and uses a derivation from the ICIQ bladder diary, which is a 3-day diary that allows subjects to record urinary frequency, volume voided, urgency and fluid intake (amount and type) [Bright 2014]. The voiding pod will automatically transfer the voiding information (i.e., volume and timepoints) to the voiding diary, and the subjects must provide additional

information (i.e., urgency, and amount and type of fluid intake). The Minze Diary Pod must be completed during the day, and it must be started in the morning, i.e., completion only starts on the first morning after Visit 1, Visit 2, and Visit 6 and lasts for 3 days; the Minze Diary Pod must also be completed for 3 full days immediately preceding Visit 4 and Visit 8. The Minze Diary Pod collects all data for the endpoints time to the first nocturnal void, change in voiding volume (nighttime and daytime) including total voiding volume, and change in number of nocturnal voids.

For all analyses below, 'pod voids' as well as 'manual voids' will be used. Only data from completed cycles will be included in the analysis. Bedtime and waketime were collected by Minze Health. Bedtime is defined as the 'exact time the subject went to sleep', and waketime is defined as the 'exact time the subject woke in the morning', according to Minze Health specifications.

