# 6.3.2.4.2 Analysis

The total voiding volume per night will be averaged across voiding nights with available data (for baseline, Week 1, and Week 4 assessments). The mean total voiding volume and corresponding changes from baseline will be summarized descriptively by visit and treatment (based on all 3 approaches as described above). In addition, the total night voiding volume **plus** the morning volume will be summarized descriptively by visit and treatment (based on data derived by Minze Health).

Analyses will be repeated for the morning voiding volume and the total daytime voiding volume based on the data provided by Minze Health.

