# 6.3.2.5.2 Analysis

Changes from baseline to post-baseline visits in the number of nocturnal voids will be analyzed using an MMRM with treatment (daridorexant 50 mg; placebo), week within period (Week 1; Week 4), and period (TP I; TP II) as factors, baseline number of nocturnal voids as covariate, and the interaction of treatment and week. The MMRM will be applied to all 3 approaches, as described above.

An unstructured covariance matrix will be used to account for the correlation between repeated measurements from the same subject. A restricted maximum likelihood approach in combination with the Newton Raphson Algorithm will be used to derive (unbiased) estimates of variance components. The Kenward-Roger approximation will be used to compute the denominator degrees of freedom and adjust standard errors [Kenward 1997]. If the analysis fails to converge, the following structures will be tested in the subsequent order until model-convergence is achieved: heterogeneous Toeplitz, Toeplitz, autoregressive, and compound symmetry.

To evaluate the efficacy hypotheses, appropriate contrasts will be used to test the treatment differences of interest (i.e., the difference in LS Mean change from baseline to Week 4 between daridorexant 50 mg and placebo).

The LS Mean for each treatment per time point will be displayed with the associated standard errors and 95% CIs. For the comparison of daridorexant with placebo, the placebo-adjusted LS Mean will be displayed with the associated standard error, 95% CI and unadjusted 2-sided p-value.

The changes from baseline in the total number of nocturnal voids will be plotted over time (averaged across the 3 nights) by treatment (based on all 3 approaches).

The number of nocturnal voids and the change in the number of nocturnal voids will be analyzed descriptively, averaged across the 3 voiding nights, by treatment and visit (based on all 3 approaches).

Descriptive analyses will be repeated for the number of daytime voids, based on the data provided by Minze Health, by treatment and visit.

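### The SAP says the vendor's day, night and morning void labels are partly wrong, but re-derives only the nocturnal endpoints and leaves both daytime endpoints on vendor data alone

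*SAP*

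**What the plan says.** - **The fault.** SAP 6.3.2.4 gives this reason for its three nocturnal volume analyses: "The rationale for the conducted analyses is the partially incorrect labelling of day, night and morning voids in the Minze Health database". It adds that a night with no recorded void may be a true zero or uncollected data. SAP 6.3.2.5, which covers nocturnal and daytime voids, refers back to the same rationale.
- **Nocturnal endpoints.** Three versions each: vendor-derived (Analysis 1), derived from bedtime and waketime (Analysis 2), and the latter with zero-void nights set to missing (Analysis 3). Volume is "summarized descriptively by visit and treatment (based on all 3 approaches as described above"). The count goes through an MMRM in all three versions, each with an unadjusted two-sided p-value.
- **Daytime endpoints.** Protocol Table 3 lists "Changes from baseline to Week 1 and Week 4 in the total daytime voiding volume assessed using the voiding diary", and SAP 6.3 lists "Change from baseline to Week 1 and Week 4 in number of daytime voids assessed using a voiding diary". For volume, SAP 6.3.2.4.2 says "Analyses will be repeated for the morning voiding volume and the total daytime voiding volume based on the data provided by Minze Health". For the count, SAP 6.3.2.5.2 says "Descriptive analyses will be repeated for the number of daytime voids, based on the data provided by Minze Health, by treatment and visit".
- **Nocturnal plus morning volume.** These analyses "will be conducted as well, but only based on data as derived by Minze Health".
- **Data held.** SAP 6.3.2 says "The voiding pod will automatically transfer the voiding information (i.e., volume and timepoints) to the voiding diary", and that the vendor collected bedtime and waketime.
- **Ranking of versions.** SAP 6.3.2.4 and 6.3.2.5 name no main version. SAP 11.4 says two sensitivity analyses were added for each nocturnal endpoint, without saying which two. SAP 5.3.2 uses the vendor-derived count in the baseline table.

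**The concern.** The SAP names all three labels as unreliable, not only the night label. A night void labelled as day lowers the nocturnal count and raises the daytime count by the same amount, and the opposite error does the reverse. One mistake can therefore enter two tables. The SAP protects the nocturnal table with a timestamp version and leaves the daytime table without one, although both could be built from the same void times, bedtime and waketime. It gives no reason why vendor data that need a check at night can stand alone by day.

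The second gap is the ranking. If the vendor version is main, as SAP 11.4 implies, the lead result for what SAP 11.3 treats as a key voiding endpoint comes from the source that the SAP itself faults. If no version is main, three p-values stand side by side with no stated order.

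At stake is how far the daytime summaries can be trusted when they are read beside the nocturnal ones. No confirmatory claim depends on them.

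**Working it through.** **Step 1: which endpoints have a version based on bedtime and waketime.** The six voiding-diary endpoints in SAP 6.3:

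| Endpoint | Source in the SAP | Bedtime/waketime version? |
|---|---|---|
| Number of nocturnal voids | 6.3.2.5, three versions | Yes |
| Total nighttime volume | 6.3.2.4, three versions | Yes |
| Time to first nocturnal void | 6.3.2.1.1 | Yes |
| Volume of first nocturnal void | 6.3.2.3 | Yes |
| Number of daytime voids | 6.3.2.5.2, vendor data | No |
| Total daytime volume | 6.3.2.4.2, vendor data | No |

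Four of six have one; the two without are the daytime endpoints. Morning volume and nocturnal-plus-morning volume are also vendor-only, but they are not in the endpoint list. In the nocturnal-plus-morning sum, swaps between the night and morning labels cancel.

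**Step 2: can the daytime versions be built?** Analysis 2 already places each void inside or outside the bedtime-to-waketime window. The voids it leaves outside, within completed cycles, are the daytime and morning voids. The missing piece is a rule for the first morning void.

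**Step 3: what the error could do.** The documents give no label error rate, so this is an illustration on assumed inputs.

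- Assumed true nocturnal means: 2.6 on placebo (equal to the screening threshold, not a Week 4 estimate) and 2.3 on daridorexant. The difference is the 0.30 of protocol 9.4.1.
- A fraction r of night voids is labelled as day, the same on both treatments. Errors in the other direction are left out.
- Vendor nocturnal difference = -0.30 × (1 - r). Spurious daytime difference = -0.30 × r. Rise in the placebo daytime level = 2.6 × r.
- Both periods share one baseline, so baseline error cancels from the treatment difference for subjects with both periods.

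| r | Vendor nocturnal difference | Spurious daytime difference | Rise in placebo daytime level |
|---|---|---|---|
| 5% | -0.285 | -0.015 | 0.13 |
| 10% | -0.27 | -0.03 | 0.26 |
| 20% | -0.24 | -0.06 | 0.52 |

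With equal error the treatment comparison barely moves; the daytime level moves more. For one subject, a single misplaced void shifts a three-night mean by 1/3 = 0.33.

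**Step 4: which nocturnal version is main.** Three versions less the two called sensitivity analyses in 11.4 leave one. The vendor version is listed first and used in 5.3.2, so it is the natural candidate, but no sentence says so. The choice matters: nights of 3, 3 and 0 voids average 6/3 = 2.0 under Analysis 2 and 6/2 = 3.0 under Analysis 3.

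**The case against.** The strongest reply has four parts.

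- **Dependence on the labels is not shown.** The SAP never says how the vendor computes its values. SAP 6.3.2.1.1 says the time-to-first-void derivation, which uses bedtime, follows the vendor's approach. The daytime sentences speak of data provided by the vendor, not derived by it. This stands as a limit: a reader might infer that the vendor daytime results are known to be wrong, and the documents do not say that. Vendor-derived remains the natural reading, since the SAP defines no daytime derivation of its own. The SAP also gives faulty labels as a reason for not relying on the vendor version alone.
- **The replacement may be no cleaner.** Bedtime and waketime come from the same vendor. If wrong bedtimes caused the mislabelling, a new derivation would repeat it. That is possible, but the sponsor already accepts this window for four of the six endpoints.
- **The scope is defensible.** The objective is nocturia, only the nocturnal count has power considerations, and the daytime outputs are descriptive. This explains the priority given to the night and keeps the point modest. It does not explain leaving listed endpoints unchecked when the data are held.
- **The main version can be worked out, and all three are reported.** Largely true. What remains is a sentence of wording, worth adding because the inferred answer is the version that the SAP faults.

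**Conclusion.** The asymmetry is real and rests on the SAP's own text. Two listed daytime endpoints have no version independent of the vendor's processing, although the stated fault covers the day label. The main nocturnal version is implied rather than stated. The effect is confined to exploratory endpoints, and its size cannot be known from the documents. If mislabelling is equal by treatment, it is small.

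Three stronger readings are not supported:

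- **That mislabelling could remove about half the planned nocturnal effect.** With r at 10% on placebo and 5% on daridorexant, the nocturnal difference is 2.3 × 0.95 - 2.6 × 0.90 = -0.155, and the spurious daytime difference is 0.115 - 0.26 = -0.145. With the rates reversed they are 2.3 × 0.90 - 2.6 × 0.95 = -0.40 and 0.23 - 0.13 = +0.10. This needs labelling error to differ by treatment in a blinded cross-over, and the documents offer no mechanism for that. Analyses 2 and 3 also already check the nocturnal count.
- **That Analysis 2 is plainly the right main version.** It counts every zero-void night as genuine and Analysis 3 counts every one as missing. The SAP says it cannot tell which is true, so choosing between them is a judgement.
- **That three p-values inflate the error of a confirmatory test.** Three independent tests at 0.05 would give 1 - 0.95³ = 0.143, but these share their data and are exploratory. Only the primary sTST hypothesis is in the testing strategy.

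**What to change.** - In SAP 6.3.2.4.2 and 6.3.2.5.2, add a descriptive version of total daytime volume and number of daytime voids derived from void timestamps: voids outside bedtime to waketime within completed cycles. State whether the first morning void counts as daytime. Keep the vendor version alongside.
- Report, by treatment and visit, how many voids carry a vendor label that disagrees with the timestamps. This would replace the assumed rates above with observed ones and show whether disagreement differs by treatment.
- In SAP 6.3.2.4 and 6.3.2.5, before unblinding, say which of the three nocturnal versions is main and why, including the reason for the handling of zero-void nights. If the vendor version is kept as main, justify it against the SAP's own statement about the labels.

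The cost is SAP wording and some programming on data already collected. A morning-void rule must be agreed, and cycles without bedtime or waketime drop out of the new tables.
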